Official title: The effects of fractional CO2 laser on Poikiloderma of Civatte

NCT number: NCT04581330

IRB Approved date: 09-09-2020

**The University of Texas Southwestern Medical Center at Dallas
Institutional Review Board**

Protocol Template (for Investigator Initiated Studies)

Title: The effects of fractional CO₂ laser on Poikiloderma of Civatte

Principal investigator: [name].

Funding Sponsor: UTSW Dept of Dermatology

IND Number (if applicable):

Version number and date: Version 1; 7/19/2020

Introduction and Purpose: This study will assess the safety and efficacy of fractional CO₂ laser treatment for Poikiloderma of Civatte (POC). POC is a chronic vascular and pigmentary disorder typically involving the lateral and inferior neck region, as well as the chest area. Clinically, poikiloderma appears as a combination of telangiectasia, irregular pigmentation, and atrophic changes¹. Previously studied effective treatments of POC include pulsed dye lasers and IPL devices.^{2,3,4,5} Ineffective treatments include hydroquinone, electrosurgery, argon laser photocoagulation, and cryotherapy.⁶ Although PDL and IPL laser technologies are relatively safe, there have been a few reports of PDL treatment with subsequent complications, which may include ulceration developing immediately after treatment as well as scarring.^{7,8,9,10} Additionally,

¹ Arielle NB Kauvar MD, Agneta Troilius MD PhD, Chapter 39. Laser and Light Treatment of Acquired and Congenital Vascular Lesions. *Surgery of the Skin*, 2005 Pages 625-644. Available online 18 September 2013.

² Haywood RM, Monk BE. Treatment of poikiloderma of Civatte with the pulsed dye laser: a series of seven cases. *J Cutan Laser Ther*. 1999;1(1):45-48. doi:10.1080/14628839950517093

³ Clark RE, Jimenez-Acosta F. Poikiloderma of Civatte. Resolution after treatment with the pulsed dye laser. *N C Med J*. 1994;55(6):234-235.

⁴ Goldman MP, Weiss RA. Treatment of poikiloderma of Civatte on the neck with an intense pulsed light source. *Plast Reconstr Surg*. 2001 May;107(6):1376-81. PubMed PMID: 11335804.

⁵ Wheeland RG, Applebaum J. Flashlamp-pumped pulsed dye laser therapy for poikiloderma of Civatte. *J Dermatol Surg Oncol*. 1990 Jan;16(1):12-6. PubMed PMID: 2299018.

⁶ Geronemus R. Poikiloderma of Civatte. *Arch Dermatol*. 1990;126(4):547-548. doi:10.1001/archderm.1990.01670280133038

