The study subjects' neck and décolletage area will be divided into two equal halves. The line of division will be from the mid mental protuberance to manubriosternal junction. One half of the neck and upper chest area will be treated with ablative fractional CO2 laser while the other half will be untreated and used as a control. If desired after the study endpoint, patients may have the other side of their neck treated at no additional charge.

Primary Outcome Measures:

Physician's Global Aesthetic Improvement Scale at 12- and 24-weeks post treatment.

Photographs will be presented to a panel of independent dermatologists. The panel will be blinded to treatment parameters and the treatment laterality at each photograph time point. Each

²⁶ Ramsdell WM. Fractional carbon dioxide laser resurfacing. *Semin Plast Surg.* 2012;26(3):125-130. doi:10.1055/s-0032-1329414

²⁷ Omi T, Numano K. The Role of the CO2 Laser and Fractional CO2 Laser in Dermatology. *Laser Ther.* 2014;23(1):49-60. doi:10.5978/islsm.14-RE-01

dermatologist will be asked to identify the baseline and post-treatment images from randomized, paired images for all subjects. Reviewers will rate improvement in POC in 10% increments on a 10-point scale (0% no improvement to 100% or complete clearance)

Secondary Outcome Measures

Subject Satisfaction Assessment at 12- and 24-weeks post treatment. Subjects will assess overall satisfaction with improvement of poikiloderma of civatte using an 5-point satisfaction and aesthetic scale.

Study subjects will be followed for 24 weeks post-laser treatment to assess incidence and severity of all procedure-related adverse events.

4. Study procedures

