Given the current pandemic, limited in-person follow-ups will be scheduled (once at baseline before treatment, then at 12 and 24-weeks post-treatment. Participants will communicate immediate post-treatment issues or concerns along with selfies through MyChart on day 2, 3, 7, 10, 14 to track progress and to identify any post procedural complications in a timely fashion. There will also be no costs to the patients for the laser procedures as funding will be supplied by the UT Southwestern Dermatology department via an educational grant. Patients desiring treatment of the control side after the study end-point (24 weeks) will be provided at no cost for the participants.

5. Sub-Study Procedures: N/A

6. Criteria for Inclusion of Subjects

- Male and female subjects, English and non-English speakers, and subjects more than 18 years old
- Clinical diagnosis of poikiloderma of Civatte affecting the neck and chest

- Agree to not undergo any other procedures on the neck and chest area during the study
- Agree to refrain from tanning for 6 months post-procedure
- Willing and able to read, understand, and sign the consent form
- Willing and able to adhere to the treatment and follow-up schedule as well as post-treatment care

7. Criteria for Exclusion of Subjects

- Patients under 18 years old
- Active skin infection, dermatitis, or a rash on the treatment area
- Pregnant or lactating patients
- Patients on immunosuppressive medications
- Any laser procedures or chemical peel procedures on the neck or chest area within the past 6 months
- Patients with multiple comorbidities such as diabetes mellitus, cardiovascular diseases, neurologic disorders, internal malignancies
- Personal history or family history of forming keloids or hypertrophic scars, or abnormal wound healing
- Patients with known bleeding disorders or taking more than one anticoagulation medications
- Undergoing any surgery in the treatment area within the past 12 months
- History of radiation to the head, neck, and chest area
- Systemic use of isotretinoin within 6 months
- Any use of gold therapy
- Current smoker or history of smoking within 12 months of study

- Any physical or mental condition in which the investigators deem unsafe for the subject to participate in the study.
- History of recurrent herpes simplex on the neck or chest.

8. Sources of Research Material

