Sources of materials used during this study will include data collected from patient surveys, data collected from blinded dermatologists' assessment, and pictures taken of the participants. These materials and data will be obtained at each patient visit. Given the current pandemic, only limited in-person follow-ups will be scheduled (once at baseline before treatment, then at 12 weeks, 24 weeks). Participants will communicate immediate post-treatment issues or concerns along with selfies through MyChart on day 2, 3, 7, 10, 14 to track progress and to identify any post-procedural complications in a timely fashion. Materials and data gathered will be obtained specifically for research purposes, and no existing records or specimens will be used.

9. Recruitment Methods and Consenting Process

Subjects will be identified from patients presenting to the dermatology department at UT Southwestern. When a patient with POC is identified, they will be offered inclusion in the study. Informed consent will be obtained. Both English and non-English speaking patients will be included. If the patient is non-English speaking, a certified translator will be used to obtain consent. Each patient will be informed that he or she has the right to withdraw consent and terminate participation in the study at any point if he or she so desires. No vulnerable populations (cognitively impaired, institutionalized, children) will be included in the study to minimize the risk of undue influence or coercion.

10. Potential Risks:

- Ocular – severe ocular complications such as corneal ulceration and cataract could happen with any laser devices. Therefore, CO2 laser specific eyewear will be provided to everyone in the treatment room. Ocular complication for this study should be low since we are mainly targeting the neck and upper chest area instead of the facial area.
- Pain – Topical anesthesia, and a forced-air cooling device will be used to help patients tolerate the procedure. Prolonged severe pain postoperatively may indicate other complications such as infection and patient should contact the investigators and will be examined in-person to determine the cause.

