- Infection – patients will be counseled on signs of infection such as increased erythema, purulence, oozing and crusting. Patients will submit electronic selfies of the treatment area electronically to investigators on day 2, 3, 5, 7 and 10. Investigators will contact patients if any signs of infection are identified. For patients with skin infection within the past 6 months, topical mupirocin ointment TID applied to the nares will be prescribed to prevent staph colonization.
- Post-inflammatory hyperpigmentation: This usually happen less frequently in lighter skin types which are the groups most commonly affected by POC. However, should this occur, hydroquinone and topical retinoids can be prescribed for the patient at the study end-point to alleviate the dyschromia.
- Prolonged erythema: if erythema lasts more than 3 weeks postoperatively, a mid-potency topical steroid will be prescribed to the patient.
- Scarring: patients with personal and family history of keloid disease and hypertrophic scar formation will be excluded from the study. If hypertrophic or keloidal scars happen, intralesional steroids will be used to flatten the scars.

11. Subject Safety and Data Monitoring

All treatments will be completed at the Dermatology clinics at UT Southwestern where there are adequate resources for medical intervention in case of an adverse event such as increased bleeding, pain, or infection. The risk of severe bleeding is minimal and does not warrant the need for spare blood products or type and screening.

12. Procedures to Maintain Confidentiality

The study materials will not be disclosed to any outside persons or entities. Patient surveys collected will be stored securely in files in the dermatology offices and will not be removed from campus.

13. Potential Benefits

- Improved overall dyschromia and telangiectasia of the chest and neck area
- Overall increased patient satisfaction and quality of life
- Provide patients safe and effective alternative for treatment of discoloration and atrophy of neck and chest area which hopefully can be generalized to similar patient populations.

14. Biostatistics

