Descriptive statistics will be used to summarize patient demographics. Count (%) will be used for categorical variables; and mean, standard deviation (SD), and range (min/max) will be used to summarize continuous variables with approximately normal distributions. Skewed continuous variables will be summarized by median and interquartile range (IQR). Outcome data will be collected on patient satisfaction assessment scores and physician's global aesthetic improvement scores, as well as assessment of adverse events. The Wilcoxon signed rank test will be used to compare the magnitude of change between the baseline scores and post-intervention scores. The Wilcoxon signed rank test will also be used to compare the magnitude of change of the treated

area and the control area. A p-score of <0.05 will be considered statistically significant. The target sample size is 10 people.

Outcome Measurement:

Global Aesthetic Improvement Scale`

| | Degree | Description |
|---|-------------------------|--|
| 1 | Exceptional improvement | Excellent corrective result |
| 2 | Very improved patient | Marked improvement of the appearance, but not completely optimal |
| 3 | Improved patient | Improvement of the appearance, better compared with the initial condition, but a touch-up is advised |
| 4 | Unaltered patient | The appearance substantially remains the same compared with the original condition |
| 5 | Worsened patient | The appearance has worsened compared with the original condition |

Patient Satisfaction Assessment

| | | | | |
|--|--|--|---|--|
|  |  |  |  |  |
|  |  |  |  |  |
| Very Unsatisfied | Unsatisfied | Neutral | Satisfied | Very Satisfied |

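### Section 10 treats erythema that lasts more than 3 weeks, but no contact is scheduled between day 14 and week 12, so cases that clear in between are captured only through patient report

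*Combined protocol and SAP*

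**What the plan says.** Section 10, in the item on prolonged erythema, states a duration rule: "if erythema lasts more than 3 weeks postoperatively, a mid-potency topical steroid will be prescribed to the patient".

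The contact schedule appears in three places:

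- Section 4 has participants send messages and selfies through MyChart "on day 2, 3, 7, 10, 14 to track progress and to identify any post procedural complications in a timely fashion".
- Section 8 repeats those days and says that "only limited in-person follow-ups will be scheduled (once at baseline before treatment, then at 12 weeks, 24 weeks").
- Section 10, in the infection item, gives a different list: "Patients will submit electronic selfies of the treatment area electronically to investigators on day 2, 3, 5, 7 and 10".

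On patient-initiated contact, the pain item of Section 10 says: "Prolonged severe pain postoperatively may indicate other complications such as infection and patient should contact the investigators and will be examined in-person". The erythema item has no counterpart.

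On what is to be measured, the introduction opens with "This study will assess the safety and efficacy of fractional" CO2 laser treatment. Section 3 lists among the secondary outcomes: "Study subjects will be followed for 24 weeks post-laser treatment to assess incidence and severity of all procedure-related adverse events". Section 14 names the satisfaction and improvement scores as outcome data, "as well as assessment of adverse events".

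**The concern.** The rule and the schedule are both explicit, and they do not meet. Under either list the selfies stop before erythema can count as prolonged by the protocol's own definition. No further contact is scheduled until long after that point.

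Two things are at stake:

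- **Care.** A patient whose redness persists and who does not write in would not be seen at a scheduled contact until week 12, so the promised steroid could start weeks late.
- **Measurement.** Safety is half of the stated purpose, and prolonged erythema is one of the few complications that the protocol names and defines by duration. If cases that clear before week 12 are known only from what patients say, a low count could mean few cases or incomplete reporting. With 10 patients, one unreported case moves the observed rate by 1/10, or 10 percentage points.

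**Working it through.** The plan gives no figure of its own here, so the check is calendar arithmetic on stated days, counted from the procedure.

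**Inputs**

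| Item | Source | Day |
|---|---|---|
| Erythema trigger | Section 10, more than 3 weeks | after 3 × 7 = 21 |
| Selfies, longer list | Sections 4 and 8 | 2, 3, 7, 10, 14 |
| Selfies, shorter list | Section 10, infection | 2, 3, 5, 7, 10 |
| Visits after treatment | Sections 4 and 8, weeks 12 and 24 | 12 × 7 = 84; 24 × 7 = 168 |

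**Step 1: last look before the trigger.** By the longer list, 21 − 14 = 7 days before it. By the shorter list, 21 − 10 = 11 days before it.

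**Step 2: interval with no scheduled contact.** By the longer list, 84 − 14 = 70 days. By the shorter list, 84 − 10 = 74 days. Under both lists, nothing is scheduled from day 15 to day 83.

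**Step 3: longest wait from trigger to next scheduled look.** 84 − 21 = 63 days, or 9 weeks, under either list.

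**Step 4: what scheduled observations can show.** Take a patient who is red at the day-14 selfie.

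- If still red at day 84, the 3-week limit has been passed, but this is first seen 63 days after the trigger.
- If clear at day 84, the duration lies somewhere between 14 and 84 days. The 3-week limit falls inside that interval, so scheduled observations cannot say whether it was passed.

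**Step 5: effect of added looks.** With a selfie at day 22, the wait from trigger to next look falls from 63 days to 22 − 21 = 1 day. A patient red at day 14 and at day 22 has passed the limit. One who is clear at day 22 has cleared by about the limit. The remaining gap to week 12 is 84 − 22 = 62 days. A further selfie at week 6 (day 42) splits it into 42 − 22 = 20 and 84 − 42 = 42 days, which narrows the duration for those still red.

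The documents do not say how long erythema lasts after this treatment or how often patients report it. The number of cases affected therefore cannot be computed from them.

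**The case against.** The strongest reply has four parts.

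1. **Adverse events are followed for 24 weeks.** Section 3 commits to this, and the only later contacts are the two visits. The natural reading is that patients are asked about adverse events there, so a cleared episode may be elicited at week 12 and not merely volunteered. This stands. What it leaves is recall of up to 12 weeks, which is still patient report. It may recover the fact of an episode, but it dates it poorly and comes too late for treatment.

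2. **The selfies are an early check.** Sections 4 and 8 tie them to immediate post-treatment problems. That softens the criticism, but the same sentence gives them the task of identifying any complication promptly, and no other scheduled contact covers the period after day 14.

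3. **Instructions may sit elsewhere, and day 14 gives a lead.** Consent pages are absent from the public copy and aftercare advice may not be reproduced in full, so an instruction to report lasting redness could exist. The infection item does counsel patients on increasing redness, but as a sign of infection. Staff who see redness on day 14 could follow it up. Nothing prevents this, and nothing in the available text requires it. The 63-day wait is thus a worst case: it needs a patient who does not write in and a day-14 photograph that nobody pursues.

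4. **The trial is small and visits were limited because of the pandemic.** This is true, and it argues for a remote remedy through the channel already in use.

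Two stronger readings are tempting. A reader might infer that steroid use before the week-12 rating distorts the efficacy comparison. The documents do not support that conclusion: the gap concerns when erythema is seen and treated, and they give no information on how many patients would receive a steroid or what it would do to the ratings. A reader might also infer that most prolonged cases will be lost from the count. That would need durations and reporting rates that the documents do not give.

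**Conclusion.** The concern holds as a gap in safety ascertainment and in timely care. The duration rule in Section 10 cannot be applied from scheduled contacts until week 12. There is no scheduled look for 70 days (74 by the shorter selfie list), and the next one falls up to 63 days after the trigger. Erythema that passes day 21 and clears before day 84 reaches the record only through an unscheduled message or recall at week 12, so its duration is not reliably known and its treatment may be late or omitted.

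These figures rest only on the stated days and on counting weeks as 7 days from the procedure. The conclusion does not extend to the primary outcome or to the planned Wilcoxon tests. The change is worth making because it is cheap; the trial's main analysis does not depend on it.

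**What to change.** 1. Add one MyChart selfie at about day 22 for every patient, and optionally one at week 6 for those still red.
2. Use one list of selfie days in Sections 4, 8 and 10.
3. Add one sentence to the erythema item telling patients to message the investigators if redness on the treated half lasts beyond 3 weeks, in parallel with the existing instruction for pain. If the consent form or aftercare sheet already says so, repeat it in the protocol.
4. Report the number of patients with erythema at each scheduled look.

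**Cost.** 10 patients × 1 selfie = 10, rising to at most 10 × 2 = 20 if every patient is still red and sends one at week 6. No in-person visit is added, so the pandemic limit on visits is kept, and the planned tests are unchanged. The downside is that a scheduled look will probably give a higher reported erythema count than patient report alone.

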Patients with a clinical diagnosis of POC defined by a skin change with atrophy, hypopigmentation, hyperpigmentation, dilation of the fine blood vessels (telangiectasia) will be recruited. Ten patients will be consented. Before the initial visit, all patients will complete a one-month preoperative daily use of SPF 50+ sunscreen. The sun protection is to reduce further sun damage and protect skin from increased photosensitivity that may occur after laser resurfacing. At the initial visit, high resolution photographs of the affected area on the neck and décolletage area will be taken. All patients will fill out a form with demographic information. Patients will be instructed to come to their appointment with clean skin and without any lotions or moisturizers on the neck or décolletage area. Laser-specific eyewear will be provided to practitioners, patients, and all other people in the treatment room. A blue skin marking pen will be used to draw a line from mid mental protuberance to manubriosternal junction to divide tested area into two equal halves. Compounded benzocaine, lidocaine, and tetracaine (BLT) cream in a 20:8:4% concentration will be applied to the treatment area for 40 minutes prior to the procedure. Before

the treatment, topical anesthesia will be thoroughly washed off with chlorhexidine gluconate and distilled water. One pass with a 1-mm spot density and a 60micron depth will be performed followed by a 1mm spot density and a 200-micron depth will be used. The other half of the testing area will be left intact and used as the control for easy comparison. The side that undergoes treatment will be selected randomly. Forced cold air (Zimmer cooler) will also be used in conjunction with the laser device for better patient comfort.

Cold compresses with refrigerated distilled water can be used to reduce swelling and to soothe the skin with frequent reapplication of white petrolatum to keep the skin coated for days 1-5 post-procedure with strict sun avoidance for the first week post-procedure. Daily use of broad-spectrum sunscreen with SPF50+ will be required after the first week.

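### Section 14 gives a before/after test, which has no defined baseline score and no comparison with the untreated side, equal standing with the treated-versus-control test

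*Combined protocol and SAP*

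**What the plan says.** Section 14 (Biostatistics) states two tests. The first is: "The Wilcoxon signed rank test will be used to compare the magnitude of change between the baseline scores and post-intervention scores". It names no side, scale or week. The next sentence applies the same test to the change in the treated area against the change in the control area. One threshold, p<0.05, covers both. The target is 10 people.

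Section 3 gives the primary outcome as "Physician's Global Aesthetic Improvement Scale at 12- and 24-weeks post treatment". It then describes a blinded panel: each "dermatologist will be asked to identify the baseline and post-treatment images from randomized, paired images for all subjects", and "Reviewers will rate improvement in POC in 10% increments on a 10-point scale (0% no improvement to 100% or complete clearance". For the secondary outcome, also at weeks 12 and 24, "Subjects will assess overall satisfaction with improvement of poikiloderma of civatte using an 5-point satisfaction and aesthetic scale".

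The GAIS table in section 14 runs from 1 to 5. Every category from 3 to 5 is defined against the starting condition, and category 4 means unaltered.

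Section 8 lists patient surveys and "data collected from blinded dermatologists' assessment" among the data sources and adds: "These materials and data will be obtained at each patient visit". One of those visits is baseline.

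**The concern.** A before/after test needs a score before and a score after. None of the three scales has a defined pre-treatment value. GAIS and the percentage rating are judgements of change, and satisfaction with improvement has no natural value before treatment. GAIS and satisfaction are scheduled only after treatment. Section 8's general sentence about visits includes baseline, but it defines no baseline item.

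For the physician scales the first test can then only ask whether the ratings differ from an implied null value: 0%, or GAIS category 4. That question does not involve the untreated half, which the design includes so that change unrelated to the laser can be removed. Because the two tests share one threshold and neither is ranked, a significant before/after result could be reported as laser efficacy even if the untreated side changed just as much.

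**Working it through.** The plan gives no power, effect size, SD or expected change on untreated skin, so there is no figure of its own to reproduce beyond n=10. All rates below are assumptions chosen to show a range.

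**Inputs.** n=10 and p<0.05 are from section 14. Two-sided testing is assumed because the plan does not say. The p-value is the exact signed-rank p, with midranks for ties and zero differences dropped.

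**GAIS, before/after.** Code each side +1 (improved), 0 (category 4) or -1 (worsened). All non-zero values tie, so p = 2 x P(Binomial(m, 0.5) <= the smaller count), with m non-zero ratings.
- 5 improved/0 worsened: 2/32 = 0.0625. 6/0: 2/64 = 0.031. 7/1: 2 x 9/256 = 0.070. 8/1: 2 x 10/512 = 0.039. 9/1: 2 x 11/1024 = 0.021.
- The rejecting patterns are 6/0, 7/0, 8/0, 9/0, 10/0, 8/1 and 9/1, and their mirror images.
- With 60% improved, 10% worsened and 30% unaltered, the multinomial probabilities in that order are 0.0794 + 0.0907 + 0.0680 + 0.0302 + 0.0060 + 0.0454 + 0.0101 = 0.330. The mirror patterns are negligible.
- The same sum gives 0.090 for 40%/10%. For 20%/20%, counting both directions, it gives 0.004.

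These results do not depend on the control side. At 60%/10% on the treated side the test rejects in 33% of trials whether the control side is at 20%/20% (a laser effect) or also at 60%/10% (none).

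**GAIS, treated-versus-control, no laser effect.** By simulation (20,000 trials per setting), with equal rates on both sides and independent sides, rejection is 1.2-1.4% at all three settings. With between-side correlation 0.5 it is 0.4-0.6%.

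**0-100% rating, no laser effect.** Ratings are Normal(drift, SD 10 or 15 points), rounded to 10. Section 3 does not say how a pair is scored when the reviewer takes the baseline image for the later one, so two rules are shown. Excluding such pairs gives the same before/after p as scoring them 0, because zeros are dropped.

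| Drift | Before/after, scored 0 | Before/after, scored negative | Treated-versus-control, either rule |
|---|---|---|---|
| 0 | 5-12% | 1.5-2.5% | 0.8-3.2% |
| 5 points | 38% | 10-15% | 1.7-3.1% |
| 10 points | 71-83% | 36-63% | 2.3-3.3% |

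The 5-12% at zero drift arises because a scale cut off at 0% can only err towards improvement.

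**Second model.** With continuous changes and between-side correlation 0.5 or 0.7, a shared change of 0.25, 0.5, 0.75 or 1.0 SD makes the before/after test reject in about 10%, 28%, 54% or 79% of trials. Treated-versus-control stays at about 5%.

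**The case against.** The strongest reply is that the plan already contains the right comparison in its next sentence, and that nothing says a before/after p-value will support an efficacy claim. The first part is true, and it limits the point to ranking the tests. The second is also true, but nothing prevents that use either. The before/after sentence names no side, so it could be run within each side; even then it makes no comparison between them.

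Next, the large-drift scenarios may not be realistic. Section 2 describes the disease as persistent, and section 4 says "all patients will complete a one-month preoperative daily use of SPF 50+ sunscreen" before the baseline photographs, which makes a further sunscreen effect less likely. This stands. The 33% needs 60% of untreated sides to be rated improved, and the 71-83% needs a 10-point common drift. Neither should be read as expected.

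A reader might infer that the treated-versus-control test cannot be run, because no sentence says ratings are made per side and the GAIS labels are worded per patient. The documents do not support that for the physician scales: the panel is blinded to laterality and a comparison of areas is planned, so side-specific ratings are implied. The gap is real for satisfaction, which is described as overall.

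A reader might also infer an 18.5% false-positive risk from two physician scales at two weeks (1 - 0.95^4 = 0.185). That is a ceiling. With coarse scores and 10 pairs each test is well below 5%: 1 - (0.988)^2(0.992)^2 = 3.9% up to 1 - (0.986)^2(0.967)^2 = 9.1% if independent. Independence is itself doubtful, since the same 10 people are rated.

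**Conclusion.** The point holds and should be fixed. Section 14 gives an uncontrolled test with no defined baseline score the same standing as the controlled one. This structural defect does not depend on any assumed rate.

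Its size does depend on assumptions. With no shared change, the before/after test is conservative on GAIS (0.4% at 20%/20%) and on a rating that allows negative values (1.5-2.5%). It reaches 5-12% on the 0-100% rating if misidentified pairs are scored 0 or excluded. With shared improvement it rises to 9% or 33% on GAIS in the settings shown, while treated-versus-control stays at about 1.2% with independent sides. The documents give no basis for saying how much shared change will occur. They do not support a claim that the trial lacks a valid test or that its false-positive rate will be high.

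**What to change.** Name the paired treated-versus-control signed-rank test of the side-specific physician ratings, on one scale at one week, as the primary efficacy test. Report before/after results for each side descriptively, with no efficacy claim from them.

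Supporting wording: state that GAIS and the panel rating are made separately for each side; state how a misidentified image pair is scored; collect satisfaction per side, or report it descriptively only.

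The cost is analysis wording, a few form lines and the loss of an easily reached p-value. Power with 10 pairs is limited. Assume independent sides with 60%/10% improved/worsened on the treated side against 20%/20% on the control side. Power is then about 20% if nobody does better than grade 3, and about 43% if treated-side improvement is spread equally over grades 1-3 with control improvement kept at grade 3. For 80%/5% against 20%/20% the figures are about 52% and 83%. On the collapsed +1/0/-1 coding, the before/after test would reject in 33% and 77% of the same trials. Positive correlation between sides helps the primary test: on that coding, correlations of 0.3-0.7 give 22-30% and 60-74%.
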